### **Study design: Prospective cohort study.**

- Pre-radiotherapy assessment at baseline and patients rendered dentally fit (i.e. free of dental disease).
- Post-radiotherapy follow-up assessments at 6 months, 12 months, and 24 months.

**Selection criteria:** Adult dentate patients (i.e. patients with natural teeth) diagnosed with a primary or secondary malignant tumour of the oral cavity, nasal cavity, sinuses, salivary glands, pharynx, or larynx\* requiring radiation treatment within Northern Ireland. \*International Classification of Diseases (ICD-10) codes C00.0-C14.8 and C30.0-32.9.

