### Exclusion criteria:

- Patients deemed to have poor prognosis, or patients to receive palliative treatment only (as advised by the Clinical Oncology team).
- Patients with less than 6 teeth before the radiotherapy start date.
- Patients with recurrent head and neck cancer, or patients receiving a repeat course of head and neck radiotherapy.
- Patients with diseases affecting tooth development (e.g. amelogenesis or dentinogenesis imperfecta) or salivary gland function (e.g. Sjogren's Syndrome).
- Patients with pre-existing trismus (mouth opening less than 35mm).

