### Clinical assessment

**-Dental caries:** The presence or absence of dental caries on each tooth will be determined using the World Health Organization's criteria and coding system, and ICDAS, and recorded in a modified version of the Oral Health Assessment Form for Adults, 2013. All surfaces of the crown and root of each tooth will be assessed by: visualisation using a mouth mirror, dental probe, adequate lighting, and compressed air from a 3-in-1 tip.

Presence or absence of dental caries on each surface will be recorded as follows (Figures 1 and 2):

Code		Condition/status	
Primary teeth	Permanent teeth	Crown	Root
A	0	0	Sound
B	1	1	Caries
C	2	2	Filled, with caries
D	3	3	Filled, no caries
E	4	—	Missing due to caries
—	5	—	Missing for any other reason
F	6	—	Fissure sealant
G	7	7	Fixed dental prosthesis abutment, special crown or veneer/implant
—	8	8	Unerupted tooth (crown)/unexposed root
—	9	9	Not recorded

Figure 1: WHO criteria and coding system

[figure not shown]

Figure 2: ICDAS coronal caries decision tree

**-Periodontal disease:** A six-point periodontal charting will be performed for all patients. Clinical attachment loss and probing pocket depths will be measured using a Williams Periodontal Probe and recorded for six sites on each tooth using the Oral Health Assessment Form. The 'Centers for Disease Control and Prevention (CDC)', in partnership with the 'American Academy of Periodontology (AAP)' workgroup definition of periodontitis will be used to identify those with active periodontal disease: 2 or more interproximal sites with attachment loss  $\geq 3$  mm, and 2 or more interproximal sites with pocket depths  $\geq 4$  mm (not on same tooth) or one site with pocket depth  $\geq 5$  mm.

**-Stimulated salivary flow rate** using paraffin pellets. Patients will chew an unflavoured paraffin pellet for 5 minutes whilst expectorating into a pre-weighed disposable specimen pot. This will be undertaken in one of the private units in the Prosthetics Department of the School of Dentistry, Belfast. Following collection, the specimen pot will be transported to the Institute of Pathology, Royal Victoria Hospital, Belfast. The mass of collected saliva will be determined using a calibrated precision weighing balance. After the calculation of salivary flow rate, each patient's saliva sample will be disposed of as clinical waste and destroyed by incineration in line with the Human Tissue Act 2004.

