## **Sample size**

Sample size calculations were conducted based upon an independent samples t-test and correlation coefficient. Assuming the standard deviation of the number of carious teeth in post-radiotherapy head and neck cancer patients is 4.0 (based upon the results of a 10-year School of Dentistry audit conducted by the applicant fellow) and comparing patients receiving over 20 Gray to the 'spared' parotid gland with those receiving under 20 Gray (based upon a 80%/20% distribution seen in the Cancer Centre radiation dose audit), we would require a total sample of 150 patients with available data to have over 80% power to detect a difference of 3.0 in the mean number of carious teeth between the under 20 Gy and over 20 Gy groups as statistically significant at the 5% level. Furthermore a sample size of 150 patients would allow 80% power to detect, as significant at the 5% level, a correlation coefficient of 0.22 for the association between radiation dose to the 'spared' parotid gland (Gy) and the number of carious teeth. Assuming 30% dropout we would therefore need to recruit 215 patients.

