## **Statistical analysis**

Primary outcome measures to be analysed include: (1) the number of carious teeth and (2) the presence of periodontal disease.

(1) Initial comparisons between the radiation dose to the 'spared' parotid gland and the number of carious teeth will be performed using independent t-tests (categorising radiation dose as <20Gy and >20Gy) and ANOVA (categorising radiation dose as <20Gy, 20-30Gy, 30-40Gy, and >40Gy) as appropriate. Adjusted analysis will be performed using multiple linear regression, with the number of carious teeth as the outcome variable, radiation dose to the 'spared' parotid gland as an explanatory variable

(categorised as above) along with potential confounding variables: dental radiation dose, oral hygiene practice, diet, and mouth opening. Without categorising radiation dose, a separate analysis will be conducted using linear regression with the number of carious teeth as the outcome variable and radiation dose to the 'spared' parotid gland (Gy) as the explanatory variable to give the increase in the number of carious teeth per 10 unit increase in Gray. If the number of carious teeth is not normally distributed transformations will be used prior to analysis or equivalent non-parametric techniques will be used.

(2) Initial comparisons of the association between radiation dose to the 'spared' parotid gland (categorised as above) and the presence of periodontal disease (Yes/No) will be performed using chi-square tests. Adjusted analysis will be performed using logistic regression with presence of periodontal disease as the outcome variable, radiation dose to the 'spared' parotid gland as the explanatory variable and dental radiation dose, oral hygiene practice, diet, smoking, medical history, and mouth opening as potential confounders.

Similar analyses will be undertaken to determine the effects of dental radiation dose and tumour location on the number of carious teeth and the presence of periodontal disease in post-radiotherapy head and neck cancer patients.

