Secondary outcomes to be analysed include: quality of life, salivary flow rate, diet, oral hygiene practice, mouth opening, xerostomia (all change from baseline); tooth loss, and denture wear. Dichotomous outcomes will be analysed using chi-square tests and logistic regression as above. Continuous outcomes will be analysed as above, apart from variables with baseline measurements, for which ANCOVA will be used to compare outcome measurements adjusting for baseline. Adjusted analyses will use multiple linear regression models as above but with baseline measurements as an additional explanatory variable.

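### Stimulated salivary flow is measured before radiotherapy but is missing from the adjusted caries model, which costs some precision and leaves a possible confounder unadjusted.

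*Combined protocol and SAP*

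**What the plan says.** The protocol's Clinical assessment section describes the saliva test at the pre-radiotherapy visit: "Patients will chew an unflavoured paraffin pellet for 5 minutes whilst expectorating into a pre-weighed disposable specimen pot". The section on post-radiotherapy assessments makes clear that saliva is collected at four appointments, one before radiotherapy and three after. The Spreadsheets section stores the results visit by visit, so the baseline value is identifiable.

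Statistical analysis, item (1), gives the adjusted caries model. Spared-parotid dose enters in bands, "along with potential confounding variables: dental radiation dose, oral hygiene practice, diet, and mouth opening". The list is closed and flow is not on it. A separate regression on continuous spared-parotid dose follows, with no covariates named. Dental dose is to be analysed in a similar way.

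Flow appears in the analysis plan only as a secondary outcome. For those outcomes, "Adjusted analyses will use multiple linear regression models as above but with baseline measurements as an additional explanatory variable". That rule puts baseline flow into the salivary-flow model and leaves the caries model unchanged.

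On eligibility, the Exclusion criteria remove patients with diseases affecting tooth development "or salivary gland function (e.g. Sjogren's Syndrome"). No minimum flow is set, and the Selection criteria admit patients with a "primary or secondary malignant tumour of the oral cavity, nasal cavity, sinuses, salivary glands, pharynx, or larynx".

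**The concern.** The study asks whether dose to the spared parotid gland is associated with later caries. By excluding salivary gland disease, the protocol already treats pre-existing salivary function as something that could disturb the answer. The exclusion reaches diagnosed disease only, so flow will still vary between patients at baseline.

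Two things could follow from leaving that variation out of the caries model. First, whatever part of the caries count baseline flow explains stays in the residual and widens the interval for the dose effect. Second, dose is set by clinical need and not by randomisation, so baseline flow may differ between dose groups. A tumour in or near a salivary gland is one conceivable route. If flow does differ, part of its effect is mixed into the dose estimate.

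Timing decides which measurement may be used. Baseline flow comes before radiation and cannot lie on the path from dose to caries. Flow at 6, 12 and 24 months can, and adjusting for it would remove part of the effect under study. The plan neither includes the first nor rules out the second.

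**Working it through.** **Inputs from the Sample size section.** "Assuming the standard deviation of the number of carious teeth in post-radiotherapy head and neck cancer patients is 4.0"; "a total sample of 150 patients with available data to have over 80% power to detect a difference of 3.0"; an 80%/20% split at 20 Gy, that is 120 and 30 patients; a correlation of 0.22 between dose and caries; significance at 5%, taken as two-sided because the document does not say.

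**Inputs not in the documents.** The correlation ρ of baseline flow with caries (assumed 0.2 to 0.5), and the association of baseline flow with dose (assumed zero for precision, varied for bias).

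**Step 1: the plan's own figures.**
- Two-group contrast: standard error = 4.0 × √(1/30 + 1/120) = 0.816. The noncentral t with 148 degrees of freedom gives power 95.5%, so the claim of over 80% is met.
- Correlation, Fisher z: atanh(0.22) × √147 = 0.2237 × 12.124 = 2.712, and Φ(2.712 − 1.960) = 77.4%. The regression t-test gives 78.4%. Both are close to the stated 80%.
- Dropout: 150 / 0.70 = 214.3, so 215, as stated.

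None of these depends on the covariate list.

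**Step 2: precision with baseline flow added, flow unrelated to dose.** The residual SD becomes 4.0 × √(1 − ρ²), the partial correlation becomes 0.22 / √(1 − ρ²), and one degree of freedom is spent.

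| Assumed ρ | SE of group difference | Power, contrast at 20 Gy | Partial r | Power, continuous slope |
|---|---|---|---|---|
| no flow term | 0.816 | 95.5% | 0.220 | 77.4% |
| 0.2 | 0.800 | 96.1% | 0.225 | 78.8% |
| 0.3 | 0.779 | 96.9% | 0.231 | 81.0% |
| 0.4 | 0.748 | 97.8% | 0.240 | 84.1% |
| 0.5 | 0.707 | 98.8% | 0.254 | 88.1% |

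The gain is about 1 to 3 points for the two-group contrast and about 1 to 11 points for the slope. The slope column applies only if the continuous-dose regression itself carries the term. No figure was worked out for the four-band model.

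**Step 3: what a dose–flow association would do.** If baseline flow and dose correlate at 0.3, the variance inflation factor is 1 / (1 − 0.09) = 1.10. This takes back some of the precision gained.

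The shift in the group difference from leaving flow out is (teeth per SD of flow) × (difference in mean baseline flow between dose groups, in SD). If flow explains 2% to 20% of caries variance, teeth per SD runs from 4.0 × √0.02 = 0.57 to 4.0 × √0.20 = 1.79.
- No difference in flow between groups: shift 0.
- 0.2 SD: 0.11 to 0.36 teeth.
- 0.5 SD: 0.28 to 0.89 teeth, or 9% to 30% of the 3.0-tooth target.

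These are absolute sizes. The sign depends on which dose group has the lower flow, and the documents do not say.

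**The case against.** The strongest reply is that the benefit is small where the plan adjusts and assumed everywhere else. The two-group contrast already has 95.5% power. The larger gain belongs to the continuous-dose regression, which the plan runs without named covariates, so adding flow to the banded model alone would not deliver it. This stands, and it is why the change must reach that regression too.

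The assumed correlations are also marginal. What counts is what flow adds over the four listed covariates, in a cohort whose range of flow the salivary-disease exclusion has narrowed. This stands too, and points to the lower end of the table.

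A reader might infer that the planned estimate is confounded and overstates the effect of radiation. The documents do not support that. They give no association of baseline flow with dose or with caries. A dose–flow correlation of 0.3 and a standardised flow coefficient of 0.4 would shift the standardised slope by 0.3 × 0.4 = 0.12, which is 55% of 0.22, but that multiplies the tops of two assumed ranges. The direction is open as well. If gland tumours lower flow and go with less dose to the spared gland, the omission would pull the estimate towards no effect.

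Tumour location is recorded, analysed as an exposure in its own right, and would address the gland-tumour route more directly. That is fair, but it would not capture low flow from other causes, and it is not on the covariate list either.

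Mouth opening, which is both restricted at entry and adjusted for, is only a loose precedent, because the plan does not say which visit's value is used.

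**Conclusion.** The omission is real: a pre-exposure measurement that the study's own logic marks as relevant to caries is collected in every patient and left out of the caries model without a stated reason. The precision lost is about 1 to 3 points of power for the contrast at 20 Gy. For the continuous-dose slope it is about 1 to 11 points, provided that regression is adjusted too. Both ranges assume flow–caries correlations of 0.2 to 0.5 and no link between flow and dose; the incremental gain is likely towards the lower end. Confounding is a possibility of unknown size and sign, and may be zero.

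This is a worthwhile, inexpensive improvement to the adjusted analysis. It does not show that the sample size is wrong or the design invalid.

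**What to change.** In Statistical analysis, item (1):
- Add baseline stimulated flow rate (continuous, pre-radiotherapy visit only) to the adjusted caries models for banded spared-parotid dose and for dental dose.
- Report an adjusted version of the continuous-dose regression that also carries it.
- State that flow at 6, 12 and 24 months is not a covariate, because it lies on the path from dose to caries.
- Keep the model without flow as a sensitivity analysis.

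The cost is a few sentences and one degree of freedom in about 150 patients, with no new data. A patient without a baseline sample would need simple imputation to stay in the model. Measurement error in flow would reduce the gain and leave some residual confounding if any exists.

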**Date of document: (Version 3 13/04/2018)**

### Clinical hypothesis

The primary hypothesis is that increased mean radiation dose to the teeth and to the 'spared' parotid gland is associated with an increase in the mean number of carious teeth and in the proportion with periodontal disease 2 years post-radiotherapy.

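### The fallback for a non-normal caries count would very probably be triggered at low mean counts and would take the primary result off the carious-teeth scale; robust analysis of the untransformed count avoids this

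*Combined protocol and SAP*

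**What the plan says.** The number of carious teeth is the first of two primary outcomes. Part (1) of the Statistical analysis section plans four analyses of it:

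- a t-test of patients below against above 20 Gy to the spared parotid;
- an ANOVA over four dose bands;
- an adjusted model: "Adjusted analysis will be performed using multiple linear regression, with the number of carious teeth as the outcome variable", with banded dose and "potential confounding variables: dental radiation dose, oral hygiene practice, diet, and mouth opening";
- a separate linear regression on uncategorised dose, naming no other explanatory variable, "to give the increase in the number of carious teeth per 10 unit increase in Gray".

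One sentence then governs all of these: "If the number of carious teeth is not normally distributed transformations will be used prior to analysis or equivalent non-parametric techniques will be used". It does not say how normality is judged, which transformation would be used, how zeros are handled, or which of the two routes comes first. It names no non-parametric counterpart to either regression.

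The rest of the document works in mean counts. The Clinical hypothesis is that higher dose "is associated with an increase in the mean number of carious teeth and in the proportion with periodontal disease 2 years post-radiotherapy". The Sample size section assumes that "the standard deviation of the number of carious teeth in post-radiotherapy head and neck cancer patients is 4.0" and powers a 3.0-tooth difference in means across an 80%/20% split of 150 patients. It gives no mean count. Under Study design, patients are treated at baseline so that they begin without active dental disease.

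**The concern.** As worded, the rule tests the distribution of the outcome itself. Neither linear regression nor a t-test at this sample size needs that distribution to be normal. A count that starts near zero, cannot go below it and has an SD of 4.0 is likely to be skewed, so the fallback could easily become the actual primary analysis.

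The scale of the primary result would then be chosen after seeing the data. A slope on a transformed count is not in teeth per 10 Gy, and a rank test gives no slope. Neither can be set beside the 3.0-tooth planning difference. In an observational cohort the adjusted model carries most of the inference, and the non-parametric route names none.

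The rule also misses the departure that matters more for the t-test, the ANOVA and ordinary regression: variance that rises with the mean, combined with very unequal groups.

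**Working it through.** **Inputs from the documents.** SD 4.0; difference 3.0 teeth; 150 evaluable patients split 80/20, so 120 above and 30 below 20 Gy; 5% level (taken as two-sided); correlation 0.22. **Assumptions, because the documents are silent:** the mean count, the shape of the distribution, the dispersion, the spread of dose, and Shapiro-Wilk at 5% as the normality check.

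**1. The plan's own power.** SE = 4.0 × √(1/30 + 1/120) = 4.0 × 0.2041 = 0.816. Power = Φ(3.0/0.816 − 1.96) = Φ(1.71) = 95.7% (exact noncentral t: 95.5%). This agrees with the stated power of over 80%.

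**2. Would the rule be triggered?** A normal curve with SD 4.0 puts Φ(−mean/4) of patients below zero teeth: 31% at mean 2, 16% at 4, 6.7% at 6, 2.3% at 8 and 0.6% at 10. Simulated samples of 150 with SD 4.0 were rejected as follows:

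| Assumed mean | Negative binomial | Beta-binomial, 12–28 teeth |
|---|---|---|
| 2 to 6 | 100% | 100% |
| 8 | about 99% | 86–100% |
| 10 | 87–88% | 42–59% with 20–28 teeth |
| 12 | 71% | 24–30% with 24–28 teeth |

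The lower rates in the last column are the near-symmetric cases; with fewer teeth the rate is higher.

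**3. Would transformation restore normality?** Not at low means. In the negative binomial samples log(y+1) is still rejected in 99–100% for means 2–6. The square root is rejected in 100% for means 2–5, 85% at 6 and 47% at 8. At means 2, 3, 4 and 5, 55%, 31%, 16% and 7% of patients have a zero count, so a plain log is not available for them. At these means an analyst following the rule is pushed towards the non-parametric route.

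**4. What each route leaves.**

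| | Teeth per 10 Gy | Mean difference in teeth | Adjusted model |
|---|---|---|---|
| As planned | yes (unadjusted) | yes | yes (banded dose) |
| Transformation | no | no | yes, on another scale |
| Non-parametric | no | no | none named |

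**5. Is the fallback needed?** I simulated skewed counts (negative binomial, SD about 4, mean 3 or 5) with dose 30 ± 12 Gy and n = 150. A correlation of 0.22 corresponds to a slope of 0.22 × 4/12 × 10 = 0.73 teeth per 10 Gy. Ordinary regression recovered 0.74 and 0.72, with type I error 4.4–5.7%. Power was 76–77% with either ordinary or HC3 standard errors. For 30 against 120 patients, the plain t-test had type I error 4.2–5.0% at equal means of 3 or 5, and 92–94% power for 3.0 teeth.

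**6. Variance rising with the mean.** The negative binomial variance is m + m²/k. For means 2 (n = 30) and 4 (n = 120) with k = 1, the variances are 6 and 20.

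- Pooled variance = (29 × 6 + 119 × 20)/148 = 17.26, SD 4.15, close to the planning value.
- Pooled SE = 4.15 × 0.2041 = 0.848.
- True SE = √(6/30 + 20/120) = 0.606.
- Ratio = 0.848/0.606 = 1.40.

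Simulation (20,000 studies) gives 1.38, interval coverage of 99.0% against 95.0% with Welch, and power of about 73% against 88%. Mann-Whitney, the likely rank substitute, also has only 73%. For means 3 and 5 with k = 2 (pooled SD 3.94), the SE is 28% too large and power is 76% against 85%.

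These are 2-tooth differences. At 3.0 teeth, pooled power was 95.0% for means 2 and 5 with k = 1, and 99.8% with k = 2. It fell to 78% for means 3 and 6 with k = 1, where the group SDs are 3.5 and 6.5, a pooled SD of about 6.

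**The case against.** A reader might infer more than the documents support, in five ways.

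- **That the fallback is almost certain to be used.** This needs a mean and a normality check that the plan does not give. In near-symmetric bounded counts at means of 10–12 the trigger rate is 24–59%. The wording refers to the count, but it does not rule out a check on residuals.
- **That no adjusted analysis would survive.** This is true only of the non-parametric route. Transformation keeps multiple linear regression with the same four confounders.
- **That an adjusted per-10-Gy estimate would be lost.** That regression names dose alone, so it is unadjusted as written; the adjusted model uses dose bands.
- **That unequal variance causes false positives.** At equal means of 2–5 with k of 1 or 2, the pooled t-test's type I error was 4.6–4.9%. When variance is larger in the larger group, its intervals are too wide, which costs precision and power only.
- **That the study is underpowered because of this.** The contrast of 73% with 88% is for 2 teeth. At the planned 3.0 teeth, power was 95% or more in the settings with SD near 4 to 5.

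It is also fair that the t-tests are labelled initial comparisons, that the sample size is unaffected, and that Welch is not free: in the same equal-mean settings its type I error was 5.4–6.2%. All of this limits the point. It does not answer the central one: the rule is keyed to the wrong feature, is unnecessary at this sample size, and moves a primary result off its planned scale.

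**Conclusion.** The point stands in qualified form, as a should-fix and a cheap improvement. If the mean caries count is about 8 teeth or lower, a formal check on the raw count would very probably fail. Following the rule would then give up the estimate in teeth per 10 Gy and the link to the mean-count hypothesis and the 3.0-tooth planning difference. Transformation leaves an adjusted model on a different scale; the non-parametric route leaves none that is named. Nothing at n = 150 makes the switch necessary.

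The variance issue is separate and secondary. Under the assumed settings with an SD near the planning value, the pooled standard error is 28–38% too large for a 2-tooth difference, and power is 9 to 15 points lower than with Welch (85 − 76 and 88 − 73). The error is conservative. The means, distributions, dispersion, dose spread and normality test are all assumptions; the documents supply only the SD, the split, the difference, the correlation and the sample size.

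**What to change.** In part (1) of the Statistical analysis section:

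- Delete the transformation/non-parametric sentence.
- State that all caries analyses use the untransformed count, with heteroscedasticity-robust (HC3) or bootstrap standard errors in the regressions and Welch versions of the initial t-test and ANOVA.
- Report mean differences and carious teeth per 10 Gy in every case.
- Pre-specify a negative binomial regression with the same confounders as a sensitivity analysis.
- Carry the same wording over to the similar caries analyses of dental dose and tumour location.

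The cost is about two sentences and a little extra analysis, with no new data and no change to the 150 evaluable patients. The one statistical downside is a slightly raised type I error for Welch with 30 skewed observations in the smaller group, about 6% in simulation.

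### The periodontal primary analysis uses one yes/no per patient with no baseline periodontal term, so it cannot separate old from new disease or register worsening, although depths in mm are charted at every visit

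*Combined protocol and SAP*

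**What the plan says.** The Clinical hypothesis section frames this outcome as an increase "in the proportion with periodontal disease 2 years post-radiotherapy". Under Clinical assessment, "A six-point periodontal charting will be performed for all patients", with attachment loss and pocket depth "recorded for six sites on each tooth using the Oral Health Assessment Form". Protocol for post radiotherapy dental assessments repeats that charting at 6, 12 and 24 months.

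The charting becomes a binary outcome through a cited rule: the CDC/AAP "workgroup definition of periodontitis will be used to identify those with active periodontal disease". In Statistical analysis (2), the initial comparisons of dose with "the presence of periodontal disease (Yes/No) will be performed using chi-square tests", and then: "Adjusted analysis will be performed using logistic regression with presence of periodontal disease as the outcome variable". The listed confounders are dental radiation dose, oral hygiene practice, diet, smoking, medical history and mouth opening. Baseline periodontal status is not among them.

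The secondary outcomes are "quality of life, salivary flow rate, diet, oral hygiene practice, mouth opening, xerostomia (all change from baseline); tooth loss, and denture wear". None is a periodontal extent, severity or change measure. For secondary variables measured at baseline the plan does adjust for the baseline value.

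**The concern.** There are two linked weaknesses. First, the model has no baseline periodontal term. If some patients already meet the case definition when radiotherapy starts, presence at 24 months counts their old disease together with new disease. Those patients also cannot contribute evidence of worsening, because their status has nowhere to go.

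Second, the mm measurements enter the analysis only through the thresholds of the case definition. Beyond that, no planned analysis uses depth, the number of affected sites, or change since baseline. A dose effect that deepens attachment loss without moving patients across the threshold would go unseen.

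At stake is what the periodontal half of the primary hypothesis can show. The sample size is justified on caries alone, so this outcome has no stated power.

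**Working it through.** **The plan's own figures.** Sample size gives 150 evaluable patients, split 80%/20% over and under 20 Gy (120 and 30), SD 4.0 and difference 3.0 carious teeth, 5% level (taken as two-sided). The standard error is 4.0 × √(1/30 + 1/120) = 0.816, and power is Φ(3.0/0.816 − 1.96) = 95.7%, so the claim of over 80% is true. 150/0.7 = 214.3, rounded up to 215. These figures concern caries; none is given for periodontal disease.

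**Can a patient be a case at baseline?**
- The case definition needs at least two interproximal sites with attachment loss of 3 mm or more. It also needs either two interproximal pockets of 4 mm or more on different teeth, or one pocket of 5 mm or more.
- The pre-radiotherapy extraction guide lists pockets above 5 mm and marginal bone loss above 50%, among other criteria, and is offered as guidance.
- Two 3 mm attachment-loss sites plus 4 mm pockets on two teeth satisfy the definition without reaching the guide's pocket criterion.
- Non-surgical periodontal treatment is one of the components that a treatment plan may include. No re-charting between that treatment and radiotherapy is described.

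The two sets of thresholds therefore leave room for retained teeth that meet the case definition at the start of follow-up.

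**Illustrative cost of the yes/no.** Assumptions not in the documents: one normally distributed patient-level score, a cut-point giving the stated prevalence, and 20% to 60% prevalence under 20 Gy.

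1. Continuous score, 30 v 120, 80% power: (1.960 + 0.842) × √(1/30 + 1/120) = 0.572 SD by the normal formula, or 0.576 SD by the noncentral t.
2. Prevalence over 20 Gy after a shift d: p₁ = Φ(z(p₀) + d).
3. Power of the two-proportion test: Φ[(p₁ − p₀ − 1.96·se₀)/se₁], with se₀ from the pooled proportion and se₁ from the separate proportions.
4. Worked case, p₀ = 0.20: p₁ = Φ(−0.842 + 0.576) = 0.395; pooled proportion (30 × 0.20 + 120 × 0.395)/150 = 0.356; se₀ = 0.0977; se₁ = 0.0856; power about 52%.
5. Relative efficiency: (0.576/d₈₀)², where d₈₀ is the shift at which the yes/no test reaches 80% power.

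| Prevalence under 20 Gy | Yes/no power at 0.576 SD | Prevalence over 20 Gy for 80% power | d₈₀ (SD) | Information lost |
|---|---|---|---|---|
| 20% | 52% | 47.0% | 0.765 | 43% |
| 30% | 59% | 58.0% | 0.726 | 37% |
| 40% | 61% | 67.7% | 0.714 | 35% |
| 50% | 62% | 76.5% | 0.721 | 36% |
| 60% | 60% | 84.2% | 0.750 | 41% |

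**Sensitivity.** By the same method the loss is 56% at 10% prevalence. A small-shift formula uses the overall case proportion p: 1 − φ(z_p)²/[p(1 − p)]. It gives 36% at p = 0.50, 51% at 0.20 and 66% at 0.10. On a logistic scale, 1 − 3p(1 − p) gives 25% at 0.50, 37% at 0.30 and 52% at 0.20.

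**The case against.** The strongest reply is that the binary outcome is deliberate. The hypothesis is about a proportion, the case definition is a cited one, and chi-square tests and logistic regression address exactly that quantity. Replacing it with mean attachment loss would change the research question. This stands, and it is why the yes/no should remain primary.

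The plan also intends patients to be free of dental disease before radiotherapy, so presence at 24 months is meant to reflect new disease. This stands only in part: the thresholds set out above do not guarantee it, and a baseline term is a cheap safeguard.

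A reader might infer that the plan discards a known share of its information, around 35% to 43%. The documents do not support that. They give no prevalence, SD or distribution for periodontal disease, and other assumptions give anything from 25% to 66%. Nor does the figure measure the loss from collapsing site-level charting, which depends on a within-patient correlation that is not given.

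A reader might also infer that a null result from any planned periodontal analysis would be uninformative. The power figures describe only the unadjusted two-group comparison. The sentence on the logistic model does not repeat the dose categories and can be read as using continuous dose, and the plan promises similar analyses for dental dose.

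Finally, an mm analysis loses sites on extracted teeth, and deep pockets and mobility are among the listed reasons for extraction after radiotherapy. That is a real limitation. It affects the yes/no outcome too, since removing diseased teeth can remove case status.

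**Conclusion.** The point holds as a weakness of efficiency and interpretation. It is not an error in, or a contradiction of, the stated hypothesis. The documents themselves establish that the periodontal primary outcome is a single status per patient without baseline adjustment, that no extent, severity or change analysis is planned, and that baseline cases are possible. How many patients would be cases at baseline cannot be estimated from the documents.

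The size is illustrative only: about 18 to 28 power points below 80% in the unadjusted comparison at a 0.58 SD shift. It rests on the assumed normal score, the 30 v 120 split and 20% to 60% prevalence under 20 Gy. It says nothing about the performance of the adjusted logistic model or of a site-level model. The change is worth making because the measurements are already being taken.

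**What to change.** - Keep the CDC/AAP yes/no proportion at 24 months as the primary periodontal outcome, and add baseline periodontal status to its logistic model. State whether that status is derived from all teeth charted at baseline or only from those kept after pre-radiotherapy extractions.
- Pre-specify beside it an analysis of 24-month interproximal attachment loss in mm, at sites charted at both visits, adjusted for the same site's baseline value, with a patient random effect and dose as a continuous variable.
- Report the number of teeth extracted since baseline by dose group next to both analyses.

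The cost is a few sentences of analysis text and site-level data entry from existing forms: six sites per tooth at two visits for up to 215 patients, which is appreciable work. No new visit or measurement is needed. The main downside is that sites on extracted teeth drop out of the mm analysis, possibly because of the outcome itself. Reporting extractions does not correct this, so the mm result must be read together with those counts. Examiner agreement is planned only as kappa, so a reliability measure for the mm readings would help readers judge the added analysis.
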